5 STATISTICAL CONSIDERATIONS

5.1 Study Design

This study is a prospective observational longitudinal study of subjects 60 years and older who are offered allogeneic HCT for treatment of hematologic malignancies. The primary objective is to design and validate a composite health assessment risk model (CHARM) to predict NRM within 1-year after allogeneic HCT. This model will incorporate the impacts of statistically important subject-related variables that could include components of the GA, frailty, comorbidity burden per the HCT-CI, and various biomarkers. We will then use the composite health assessment risk model (CHARM) to describe differences in trajectories of secondary outcomes of quality of life, frailty, nursing-home admissions and disability among groups of subjects with different scores.

5.2 Accrual and Study Duration

In 2012-2016, there were 2870 subjects transplanted in BMT CTN Core Centers and 1648 transplanted in active Affiliate Centers who were 60 years and older and undergoing first allogeneic HCT for hematologic malignancies. This translates into a total of 4,518 subjects aged 60 years and older given allogeneic HCT at both Core and Affiliate BMT centers for an annual number of about ~900 subjects. With the consistent annual increase in number of older subjects given allogeneic HCT, we anticipate the actual annual number to be closer to 1000 subjects during the conduct of this study.

We expect the study to be open at all BMT CTN Core Centers (except for the Pediatric BMT Consortium) in addition to a selected group of Affiliate Centers. We anticipate that the number of centers that will open the study will make it available for ~90% of the 1000 subjects, for a total of 900 annual subjects.

Second, we anticipate that among the approximately 900 subjects aged 60 years or older offered allogeneic HCT at these centers, we estimate 60% to be enrolled and sign consent form for a total of 550 subjects. While this number is higher than usually assumed for BMT CTN trials, it is justified here given the observational (non-interventional) nature of this study, the few exclusion criteria, and the fact that most of the transplantation procedure will follow standard center practice. Given the possibility of change in transplant indication or timing, we anticipate about 20% of that sample (n=550) will not proceed to transplant and hence will not contribute to final model design. The remaining sample (80%) expected to receive the transplant and hence contribute to model development is about 440 subjects annually.

Assuming 440 subjects enrolled and given HCT per year, which is about 37 subjects per month, the study will require 24 months to recruit the target sample size of n=880 subjects. This is similar to the accrual rate for BMT CTN 0902, a similarly inclusive and minimally burdensome protocol which accrued 711 subjects over 18 months. All subjects will be followed for a

minimum of 1 year; therefore, the total study duration is expected to be 3 years. Subjects who do not complete all baseline assessments will continue to be followed. The proportion of patients who do not go on to transplant will be monitored. If the proportion is substantially higher than expected (20%) we will explore the reasons why and consider adjusting the accrual period needed to reach 880 evaluable patients.

5.3 Primary Endpoint

The primary endpoint is NRM at 1 year. NRM is defined as time to death without evidence of disease progression or recurrence from transplant. Disease progression or recurrence will be considered competing events. Subjects alive without progression or recurrence will be considered censored at the date of last follow-up.

5.4 Primary Hypothesis

A validated composite health risk assessment score comprising a combination of comorbidities, one or more components of a GA, and biomarkers will optimally risk-stratify mortality within one year after allogeneic transplant.

5.5 Sample Size and Power Considerations

Sample size calculation is based on the ratio of the number of NRM events divided by the number of potential (candidate) predictors. This ratio is known as events per variable or simply EPV. An EPV in the range of 10-15 is widely advocated as a rule of thumb for Cox proportional hazards regression models with higher EPV recommended when there are predictors with low prevalence. Concato et al. and Peduzzi et al. encouraged the use of an EPV of at least 10 for Cox regression-based prediction models.^{58, 59} Ogundimu et al. recommend using EPVs greater than 10 to calculate sample size especially when low-prevalence predictors are present in a model to eliminate bias in regression coefficients and improve predictive accuracy.⁶⁰ Since we expect modest prevalence of our proposed predictors of 15-40%, we will use an EPV of 12. The NRM rate in our subject population is estimated to be 22% (upper limit of the 95% confidence interval) based on CIBMTR data for Core and Affiliate Centers. There are 13 variables to be tested for inclusion in the model and an additional 3 variables for adjustment with a total of 16 variables. Per the equation: $(N \times 22\%) / 16 = 12$ EPV, we will need a sample size of 880 subjects. We will use this entire cohort to develop our model.⁶¹ To provide additional support for the sample size calculation beyond the events per variable approach Table 5.5 was created. Given a sample size of 880 patients, under a simple Cox regression model with a single binary predictor, we will have 80% power to detect the hazard ratios as shown in Table 5.5 using a two-sided score test with a significance level of 0.05 assuming a R-square of 0.30.

Table 5.5. Detectable Hazard Ratios for Each Binary Predictor

| | | | | | |
|---|------|------|------|------|------|
| Estimated frequency of binary predictor | 0.15 | 0.20 | 0.25 | 0.30 | 0.40 |
| Hazard ratio | 1.96 | 1.83 | 1.75 | 1.69 | 1.63 |

5.6 Demographic and Baseline Characteristics

Demographics and baseline characteristics will be summarized for all subjects. In addition to the variables being utilized for the risk score development in Table 5.9.1, other characteristics to be examined are: age, gender, race/ethnicity, primary disease, disease-specific risk categories per Disease-risk index (DRI), donor type and HLA matching, stem cell source, donor/recipient CMV status, donor/recipient sex match, and intensity of conditioning regimen.

5.7 Analysis of Primary Endpoint

5.7.1 Analysis of the Primary Endpoint

Incidence of NRM at Days 100, 180 and 1 year will be estimated using the cumulative incidence estimate, treating disease relapse or progression as a competing event. The primary method for building a composite health risk assessment score to predict NRM will be based on using a multivariate Cox proportional hazards regression model for the cause-specific hazard of NRM. We will fit this predictive model with potential covariates as described in Table 5.9.1 and explore different cut-points for predictors. Proportional hazards assumptions will be assessed for each variable using graphical approaches and time-dependent covariates; if proportional hazards are violated, time-dependent covariates will be used. Variable selection for the Cox regression model will be done using a step-wise model building approach for all multivariate models. After stepwise variable selection is complete, we will further assess the contribution of each of the final variables selected in the model to the predictive performance. This will be done by computing C-statistics and Brier scores for this final model, as well as simpler models obtained by dropping one variable at a time. We will use this information to assess whether further pruning of the variables in the risk score is indicated due to lack of contribution to predictive performance despite statistical significance.

A composite health risk score will be constructed from the final Cox model by summing the log hazard ratios for each of the relevant covariates to be included in the scoring system. We will also consider approximating the score by replacing the log hazard ratios with a numeric scoring system for ease of clinical use and will consider the creation of up to 3 groups based on tertiles of this score to facilitate summarizing the effects through cumulative incidence curves by group. The following baseline variables will be kept/forced into the multivariate model during the modeling process: donor type and HLA matching, donor/recipient CMV status and intensity of conditioning regimen. While these baseline variables will be used to adjust the multivariate model, they will not contribute to the scores created for the final CHARM. Specifically, we will only use the linear predictors ($X\beta$ terms) corresponding to the variables from Table 5.9.1 to construct the final CHARM score. Other baseline variables, as mentioned before, will be included in the multivariate regression model to account for additional differences in risk related to transplant or donor matching issues but not used to construct the CHARM score. We anticipate that there will be missing data among the CHARM variables. Therefore, multiple imputation methods may be used before developing the CHARM score.

Although the Cox regression model will be the primary method of analysis, we plan on investigating an alternative secondary prediction model using machine learning techniques such as CoxBoost.⁶¹ CoxBoost utilizes boosting along with a flexible penalization of covariates to build prediction models for survival and competing risks data in a proportional hazards

framework. It can handle potentially high-dimensional and diverse clinical and biomarker covariates. The number of boosting steps and the number of path algorithm steps will be tuned through cross-validation. The original bootstrap is not a particularly good estimator for cross validation. Therefore, we will compare and contrast the prediction performance of the primary and secondary models using 632+ bootstrap cross-validation as detailed below.⁶² The 632+ bootstrap is a weighted average of the leave-one-out bootstrap estimator and the naïve estimate of prediction error using weights 0.632 and 0.368, respectively.

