Tufts Medical Center
Oklahoma University Medicine
University of Massachusetts Memorial
Medical Center
University of Chicago Medicine
University of Kansas
University of Nebraska
University of Wisconsin
Wake Forest Baptist Health
West Virginia University

PROTOCOL SYNOPSIS

Composite Health Assessment Model for Older Adults: Applying Pre-transplant Comorbidity, Geriatric Assessment and Biomarkers to Predict Non-Relapse Mortality after Allogeneic Transplantation

Co-Principal Investigators: [name], MS and [name], MSc

Study Design: Prospective observational multicenter study of allogeneic Hematopoietic Stem Cell Transplantation (HCT) in recipients 60 years and older to assess important determinants of health status to be combined into a composite health risk model to improve risk assessment of non-relapse mortality (NRM).

At baseline, standardized Geriatric Assessment (GA) tools incorporating subject reported data and bedside testing will be collected. HCT-Comorbidity Index (CI) scores will be assigned and C-reactive protein (CRP) and albumin will be measured locally. Serial measures at 3, 6, and 12 months for frailty, skilled facility admission, and quality of life (QOL) using PROMIS measures for physical function, depression and anxiety will be determined. Graft Versus Host Disease (GVHD) through one year, serious toxicities through day 100, cognitive status at day 100 and causes of death will be captured.

Primary Objective: To determine the set of assessments and biomarkers that could together constitute a robust and valid composite health risk model for accurate personalized estimation of one year NRM.

Secondary Objectives: To determine the association of the composite health risk-model with differences in overall survival, frailty, disability, skilled-facility admission, cognitive decline, QOL and acute and chronic GVHD over the first year after transplant and with one year survival and with serious organ toxicity through day 100.

Eligibility Criteria: Subjects 60 years of age or older able to speak and read English, Spanish or Mandarin and eligible for first allogeneic transplantation based on institutional standards. Subjects must have a planned allogeneic transplantation for a hematologic malignancy. Any allogeneic graft source or donor type will be permitted. Subjects must provide informed consent.

Treatment Description:

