2.2.2 Primary Objective

To determine the set of assessments and biomarkers that could together constitute a robust and valid composite health risk model for accurate personalized estimation of NRM.

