5.7.2 Model Validation

A common way to estimate prediction error is to randomly split the sample into training and a validation set. The disadvantage of this is that not all data is available for model building and parameter estimation. Instead, we will employ the 632+ bootstrap cross-validation method to estimate the prediction error and explained variation using the approach by Schemper and Henderson.⁶³

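### The primary objective promises a personalized one-year NRM estimate, but the primary method yields a relative score from one cause-specific hazard, which does not determine that probability when relapse competes

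*Protocol*

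**What the plan says.** The synopsis states the aim as a "robust and valid composite health risk model for accurate personalized estimation of one year NRM". Section 2.2.2 repeats it without the one-year horizon. On competing risks, section 5.3 says: "Disease progression or recurrence will be considered competing events".

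The primary method in section 5.7.1 is to build the score "using a multivariate Cox proportional hazards regression model for the cause-specific hazard of NRM". The deliverable follows: "A composite health risk score will be constructed from the final Cox model by summing the log hazard ratios". Only the Table 5.9.1 variables contribute. Donor type and HLA matching, CMV status and conditioning intensity are forced into the model but left out of the score.

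For absolute risk, section 5.7.1 plans the cumulative incidence of NRM overall at days 100 and 180 and at one year, with relapse competing. It will consider curves for up to three tertile groups of the score. It also plans a secondary CoxBoost model, described as able to handle competing-risks data.

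For performance, section 5.7.1 uses C-statistics and Brier scores to decide whether variables are pruned from the final model. In section 5.7.2, "we will employ the 632+ bootstrap cross-validation method to estimate the prediction error and explained variation", with a measure whose cited source concerns Cox regression.

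On proportional hazards, section 5.7.1 says: "if proportional hazards are violated, time-dependent covariates will be used".

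**The concern.** With relapse competing, the chance of dying without relapse within a year depends on two hazards: that of NRM and that of relapse, which removes subjects from risk of NRM. The score reflects only the first. It has no baseline hazard and no relapse component, and it omits the three adjusters. Two subjects with the same score and different relapse hazards have different one-year NRM.

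Two consequences follow from what the protocol fixes. First, the objective promises an individual estimate while the method delivers a relative ranking. Second, pruning, validation and the comparison with CoxBoost all rest on measures that need a predicted probability (the Brier score and prediction error), and the primary model as specified does not supply the right one.

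A separate conflict lies within section 5.7.1. A covariate given a time-dependent effect has no single log hazard ratio, so the summing rule cannot be applied to it.

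At stake is the figure that physicians and older patients would use in counselling, and the evidence that the figure is accurate.

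**Working it through.** **1. The plan's own figures reproduce and are unaffected.**

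- Sample size (section 5.5): N = 16 × 12 / 0.22 = 872.7, against 880 stated.
- Table 5.5, with D = 880 × 0.22 = 193.6 events and R-square 0.30: HR = exp[(z0.975 + z0.80) / √(D·p(1−p)·(1−0.30))]. For p = 0.15, 0.20, 0.25, 0.30 and 0.40 this gives 1.962, 1.825, 1.743, 1.691 and 1.634, against 1.96, 1.83, 1.75, 1.69 and 1.63 stated.

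**2. Inputs for the size of the problem (Table 5.9.2).** Treatment-related mortality in that table is taken as NRM, and age groups are weighted by N (1617, 1817, 704 and 81; total 4219).

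- One-year NRM: weighted mean of 18, 21, 26 and 29% = 20.8%.
- One-year overall survival: weighted mean of 63, 61, 57 and 57% = 61.0%.
- Deaths not counted as NRM: 100 − 61.0 − 20.8 = about 18%. These deaths follow relapse, so one-year relapse is at least about 18%.

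The protocol gives no one-year relapse incidence. I assume 30%, with a range of 18% to 40%, and constant hazards within the year.

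**3. Formulas.** Let F1 be one-year NRM and F2 one-year relapse.

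- Total hazard T = −ln(1 − F1 − F2)
- NRM hazard h1 = T × F1/(F1 + F2); relapse hazard h2 = T − h1
- Single-event Cox reading: 1 − exp(−h1)
- Cumulative incidence of NRM: h1/(h1 + h2) × [1 − exp(−(h1 + h2))]

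**4. Average subject, F1 = 20.8%.**

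| Assumed relapse | T | h1 | Single-event reading | Cumulative incidence | Gap, points |
|---|---|---|---|---|---|
| 18% | 0.491 | 0.263 | 23.1% | 20.8% | 2.3 |
| 30% | 0.709 | 0.290 | 25.2% | 20.8% | 4.4 |
| 40% | 0.937 | 0.320 | 27.4% | 20.8% | 6.6 |

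Starting from the protocol's planning value of 22% instead, the single-event reading is 24.5% to 29.1% over the same relapse range.

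**5. High-risk subjects.** With 30% relapse, the relapse hazard held at h2 = 0.419 and the NRM hazard multiplied:

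| NRM hazard | Single-event reading | Cumulative incidence | Gap, points |
|---|---|---|---|
| ×1 | 25.2% | 20.8% | 4.4 |
| ×2 | 44.1% | 36.7% | about 7 |
| ×3 | 58.2% | 48.9% | about 9 |

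The gap widens in points. The ratio of the two readings does not: it falls slightly, from 1.21 to 1.19.

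**6. Same score, different relapse hazard.** Take 22% NRM and 30% relapse at reference, and fix the NRM hazard. When the relapse hazard is multiplied by 0.5, 1, 2 and 3, one-year NRM is 24.2%, 22.0%, 18.4% and 15.6%. The NRM score and the single-event reading (26.7%) are the same in all four cases. This step needs no assumption about how a later analysis would convert the score.

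**The case against.** The strongest reply has four parts.

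**No direct conversion is planned.** A reader might infer that the trial will convert the NRM hazard directly and so report inflated risks. The documents do not support this. No section proposes that conversion, relapse is treated as competing throughout, and NRM itself is estimated by cumulative incidence. The overstatement is therefore conditional.

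**The plan is not limited to a ranking.** A reader might infer that tertile curves are the only absolute risks and that calibration is wholly ignored. Neither is right. Overall cumulative incidence is planned, CoxBoost is described as suited to competing risks, and Brier score and prediction error penalize miscalibration in part. But the cumulative incidence estimates are for groups, CoxBoost is a secondary model, and only a separate assessment of calibration goes unmentioned.

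**Details may sit in a statistical analysis plan.** How hazards are combined and which Brier estimator is used are often left there, and that document is not shown. The absence of those details is not the finding. The finding is that the stated objective and the stated primary deliverable do not match, and that two rules in section 5.7.1 conflict.

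**The working aim is stratification.** Section 5.4 speaks of risk stratification, for which a cause-specific Cox model is a legitimate basis. That stands, and the model should be kept. The synopsis and section 2.2.2 nevertheless promise personalized estimation.

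**Conclusion.** The point holds as a mismatch between objective and method that should be corrected. Followed as written, the primary analysis yields a ranking by NRM hazard, not an individual one-year NRM probability. The Brier scores used for pruning and the prediction error used for validation need a probability that this single-hazard model cannot correctly supply.

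If the single-event Cox curve were used to fill the gap, average risk would be overstated by about 2 to 7 points (23% to 27% against 20.8%). With 30% relapse, the excess would be about 7 points at twice the NRM hazard and 9 points at three times. These sizes rest on constant hazards, an assumed relapse incidence and, for high-risk subjects, an unchanged relapse hazard. They describe a possible misuse, not a planned step.

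The conflict between allowing time-dependent effects and summing one log hazard ratio per covariate is real, but takes effect only if proportional hazards fail for a selected variable. Sample size and Table 5.5 are unaffected.

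**What to change.** Keep the cause-specific NRM Cox model as the basis of the CHARM score, and add:

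1. A cause-specific Cox model for relapse, using the CHARM variables, the three adjusters and the disease risk index (already listed in section 5.6). Combine it with the NRM model into each subject's one-year cumulative incidence of NRM. Another competing-risk model, such as a subdistribution model, would also serve.
2. A statement that this cumulative incidence is the probability used for pruning, validation and the comparison with CoxBoost. Report the one-year Brier score, discrimination and a calibration curve in competing-risk form, from the cross-validated predictions.
3. A rule for a covariate with a time-varying effect, for example that its average log hazard ratio over the first year enters the score.

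If the sponsor does not want individual probabilities, the alternative is to restrict the objective in the synopsis and section 2.2.2 to risk stratification. Item 3 is still needed, as is a statement of which probability enters the Brier score.

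The cost is protocol or analysis-plan wording and some extra analysis with standard methods. Relapse is already captured on the CIBMTR forms, so no new data are needed. One consequence should be stated openly: the individual probability would depend on the adjusters and the disease risk index, while the CHARM score would not.

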5.7.2 Model Validation

A common way to estimate prediction error is to randomly split the sample into training and a validation set. The disadvantage of this is that not all data is available for model building and parameter estimation. Instead, we will employ the 632+ bootstrap cross-validation method to estimate the prediction error and explained variation using the approach by Schemper and Henderson.⁶³

5.8 Analysis of Secondary Endpoints

Three risk groups will be formed, based on the tertiles of the CHARM risk score. We will provide univariate summaries of each of the secondary outcomes by CHARM score risk group for each endpoint. We will then compare the risk groups multivariate models developed for each outcome separately as detailed below. All the demographic and baseline characteristics described in section 5.6 above will be considered via stepwise variable selection for inclusion in the model. Assuming an overall type I error of 10%, a significance level of 1% will be used for all secondary analyses based on Bonferroni adjustment since we will be considering 10 endpoints between section 5.8.1 and 5.8.9. A sensitivity analyses will also be done base on the CHARM score as a quantitative measure rather than tertile groups.

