2.4.4 Consent, Enrollment and Evaluable Subjects

Enrollment for the purposes of the study will begin when the subject has completed the consent process. Subjects consenting but who did not undergo HCT will be considered exited from the study on the date this determination is made and will not be considered part of our evaluable

population. Evaluable subjects for the primary and secondary endpoints will be those who receive HCT. All subjects who sign the Informed Consent Form will be counted against the enrollment ceiling. Relapse is an important study outcome and subjects with relapsed disease will remain on the study. Data will continue to be collected from subjects with relapsed disease, to the extent possible, per the study assessment schedule (Table 4.2.4).

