5.8.1 Overall Survival

Kaplan-Meier curves will be constructed to estimate overall survival probabilities. A multivariate Cox regression model for the risk of death will be developed to estimate hazard ratios for the CHARM risk groups after adjustment for baseline characteristics as described above.

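### Section 5.8 lets CHARM be adjusted for its own components, and its overall-survival test reuses the deaths to which CHARM was fitted

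*Protocol*

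**What the plan says.** **Adjusters.** Section 5.8 sets the candidate list for the secondary models: "All the demographic and baseline characteristics described in section 5.6 above will be considered via stepwise variable selection for inclusion in the model". Section 5.6 begins: "In addition to the variables being utilized for the risk score development in Table 5.9.1, other characteristics to be examined are: age". Table 5.9.1 also lists age (70+) as a CHARM candidate. Section 5.8.1 then plans a Cox model to "estimate hazard ratios for the CHARM risk groups after adjustment for baseline characteristics as described above". Nothing in 5.8 removes CHARM's components from the list.

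**Sample.** Section 5.5: "We will use this entire cohort to develop our model". Section 2.4.4: "Evaluable subjects for the primary and secondary endpoints will be those who receive HCT". The development set and the secondary-analysis set are therefore the same people.

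**Score.** Section 5.7.1: "Variable selection for the Cox regression model will be done using a step-wise model building approach for all multivariate models" and "A composite health risk score will be constructed from the final Cox model by summing the log hazard ratios". The outcome of that Cox model is non-relapse mortality (NRM). Section 5.8: "Three risk groups will be formed, based on the tertiles of the CHARM risk score". Each secondary test is run at 1%. OS (section 3.2.1) counts death from any cause. The 632+ bootstrap in section 5.7.2 is directed at prediction error and explained variation; section 5.8 does not apply it to the secondary tests.

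**The concern.** There are two separate problems, and they pull in opposite directions.

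First, CHARM is a weighted sum of Table 5.9.1 variables. If those variables can also enter a model beside the CHARM tertiles, the tertile coefficient no longer measures the score. It measures what is left after part of the score has been taken out. The hazard ratio shrinks, its standard error grows and power falls.

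Second, the weights are chosen to fit the NRM deaths in this cohort, chance patterns included. Every NRM death is also an OS event. Testing the tertiles on OS in the same subjects therefore counts part of that chance fit as evidence. The hazard ratio is too high and the 1% level is not kept. Survival after acute GVHD (section 5.8.10) shares deaths in the same way.

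OS is the first secondary objective listed in section 2.2.3, so this result will be read as a test of whether CHARM predicts survival.

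**Working it through.** **Step 1: the plan's own figures.** Bonferroni: 0.10/10 = 0.01, as stated. Sample size: 12 x 16/0.22 = 872.7, against 880 stated; 880 x 0.22/16 = 12.1 events per variable. Table 5.5: HR = exp[(1.96 + 0.84)/sqrt(D(1 - R²)p(1 - p))], with D = 880 x 0.22 = 193.6 and R² = 0.30, gives 1.96, 1.83, 1.74, 1.69 and 1.63, against 1.96, 1.83, 1.75, 1.69 and 1.63. All reproduce.

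**Step 2: overlap of events.** Table 5.9.2, 1-year OS weighted by number evaluable: (63 x 1617 + 61 x 1816 + 57 x 704 + 57 x 81)/4218 = 61.0%, so about 39% die. With 22% NRM (section 5.5), NRM deaths are 22/39 = 56% of OS events.

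**Step 3: simulation set-up.** 880 subjects; 13 binary predictors at the Table 5.9.1 frequencies (blanks assumed at 15-40%); three forced covariates; NRM about 22%, deaths about 39%. A stepwise cause-specific Cox model for NRM gives the log-HR score, the score is cut into tertiles, and the tertiles are tested on OS at 1%. The protocol gives neither a stepwise threshold nor a correlation among predictors, nor a relapse rate. These are assumptions: thresholds 0.05 and 0.15, independent predictors, 1-year relapse 30%, constant hazards. Further runs used a 5% threshold with backward selection, or a latent correlation of 0.3 (in one of these, NRM about 20% and deaths 37%).

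**Step 4: components offered as stepwise adjusters.** OS hazard ratio, top versus bottom tertile, same subjects:

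| True effects | Correlation | Rule | Without components | Components offered |
|---|---|---|---|---|
| Table 5.9.1 HRs | none | stepwise or forward, 0.05 | 2.4 | 2.2 |
| Table 5.9.1 HRs | none | stepwise, 0.15 | 2.44 | 1.53 |
| Table 5.9.1 HRs | none | backward, 5% | 2.4-2.6 | 1.4 |
| half the log-HRs | none | stepwise, 0.05 | 1.61 | 1.59 |
| half the log-HRs | 0.3 | 5% | 2.1-2.2 | 1.3-1.35 |
| Table 5.9.1 HRs | 0.3 | 5% | 3.25-4.2 | 0.54-0.6 |

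In the 0.15 row a mean of 4.2 components entered, the standard error rose from 0.138 to 0.189, and rejection fell from 100% to 67%. Adjusting for age alone moved the hazard ratio only from 2.09 to 2.03 (half effects, correlation 0.3).

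**Step 5: reuse of the sample, no true effect.** Rejection of the OS test at nominal 1%:

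| Rule | All trials | Trials that form a score |
|---|---|---|
| stepwise, 0.05 (1,500 runs) | 8.1% | 16.6% |
| stepwise, 0.15 (1,500 runs) | 15.5% | 17.5% |
| backward, 5% (separate runs) | 4-8% | 8-15% |

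The mean hazard ratio is about 1.25-1.3 instead of 1.00. The same scores applied to 880 new subjects reject in 0.7% (0.05) and 1.2% (0.15), with hazard ratios of 0.99-1.00. For an endpoint unrelated to NRM, the same-sample test rejects in 1.2% of 1,341 runs, so there is no inflation. Monte Carlo error in the 1,500-run null rates is about 0.7-1.4 points.

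**Step 6: reuse when effects are real.** With the Table 5.9.1 HRs and independent predictors: 2.39 against 2.15 in new subjects (2.39/2.15 = 1.11) and 2.44 against 2.21 (1.10); every run rejects either way. With half the log-HRs: 1.61 against 1.32 (1.22), and rejection 77% against 25%.

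**Step 7: does cross-fitting repair the test?** Tertiles from 10-fold cross-fitted scores with the ordinary 2-df test rejected in 1.9% (backward selection) and 2.7% (all 13 kept) of 1,200 null runs, standard error about 0.4-0.5 points. A smaller run of 150 scored trials gave 0.7%. Cross-fitting removes most of the excess, but the larger runs do not show the 1% level restored.

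**The case against.** **The adjuster list can be read more narrowly.** Section 5.6 separates the Table 5.9.1 variables from the further characteristics it goes on to name. Sections 5.8.2 and 5.8.3 give the individual predictors a separate model in place of the score. This suggests that score and components were not meant to share a model, and that stands as evidence of intent. Section 5.8 does not say so, however, and age is in both lists on either reading, though age alone matters little. A SAP, not at hand, may narrow the list; the protocol sentence still permits the mixture.

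**A complete null is unlikely.** A footnote to Table 5.9.1 claims at least two supporting studies each for age, HCT-CI, KPS, CRP and albumin. This stands: the null rates show that the stated 1% is not kept, not that a positive OS result would probably be false.

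**The primary analysis is untouched.** The NRM model and its bootstrap validation are unaffected. Univariate summaries and Kaplan-Meier curves by risk group are also planned, and these are free of component adjustment, though not of reuse. A reader might infer that nothing can be learned about CHARM and OS; that goes too far.

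**Larger figures can be produced.** Keeping all 13 predictors gives 32% null rejection at 1%, but section 5.7.1 plans selection, so that is not the planned analysis.

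**Conclusion.** The plan should be corrected on both points, within limits.

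**Adjusters.** On its plain reading, section 5.8 allows CHARM tertiles to be adjusted for CHARM's own components in every secondary model that uses the list. The loss ranges from negligible to large, depending on the stepwise threshold and on how the predictors correlate, and the protocol fixes neither. A reader might infer that the CHARM effect would reverse. A hazard ratio below 1 appeared only with the full Table 5.9.1 HRs and an assumed correlation of 0.3; independent predictors gave no reversal.

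**Reuse.** For OS the 1% level does not hold under the null, and the same-sample hazard ratio is optimistic: by about 5-15% if the Table 5.9.1 HRs are true, in which case the conclusion stands, and by more if effects are weaker. Section 5.8.10 shares deaths by the same mechanism but was not simulated. A reader might infer that all the secondary 1% tests are invalid. The documents do not support that: reuse inflates a test only so far as the endpoint overlaps with NRM, and most of the secondary endpoints are not built from NRM deaths.

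The sizes rest on the simulation assumptions; the overlap of subjects, deaths and variables rests on the text alone.

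**What to change.** 1. State in section 5.8 that all Table 5.9.1 variables, including age, are excluded from the adjuster candidates in any model containing CHARM. The remaining section 5.6 characteristics stay. Keep the separate individual-predictor models in 5.8.2 and 5.8.3.
2. For OS and section 5.8.10, report hazard ratios for tertiles of a cross-fitted or out-of-bag CHARM score, in which each subject's score comes from a model built without that subject.
3. Take the p-value for those two endpoints from a permutation or bootstrap that repeats selection, scoring and testing as one sequence, since the ordinary test on cross-fitted tertiles still rejected in about 2-3% of null runs.
4. Label any uncorrected same-sample hazard ratio for these endpoints as apparent.

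Cost: protocol or SAP wording and computing time; no new data. The hazard ratios will be slightly smaller, and the pooled cross-fitted score comes from several fitted models rather than from the one final CHARM, which the report should say.
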